## 1.2 Rationale for the Current Study

HER2-targeted approaches have revolutionized the treatment and outcomes associated with HER2-overexpressing breast cancer. However, *de novo* and acquired resistance to HER2-directed approaches remains a clinical challenge, and many metastatic breast cancer patients continue to progress or relapse, despite having initially responded to treatment. Several resistance mechanisms have been described, including mutations in other signaling pathways and expression of a truncated form of HER2 [13]. Therefore, there remains an unmet need to develop novel treatment approaches for HER2-positive breast cancer that can improve clinical outcomes, particularly in the context of strategies to overcome resistance to HER2-targeted therapy.

Poziotinib is an orally administered, irreversible pan-HER inhibitor with activity against HER1, (ErbB1; EGFR), HER2 (ErbB2), and HER4 (ErbB4), as well as HER receptor mutations. The clinical results and safety profile of poziotinib to date in various studies involving patients with relapsed or refractory solid tumors as either a single agent or as combination therapy, have been very promising. These data support the expectation that poziotinib will be efficacious and well tolerated in HER2-positive metastatic breast cancer patients.

In Phase 1 studies, the MTD of poziotinib was determined to be 18 mg for continuous daily dosing and 24 mg for intermittent dosing (14 days on treatment, 7 days off treatment). The most commonly occurring toxicities included diarrhea, rash, and stomatitis, which is consistent with the known toxicity profile of other EGFR inhibitors. For monoclonal antibody EGFR-targeted therapies, such as cetuximab or panitumumab, rates of Grade 2 diarrhea are up to 21% and for Grade 3 diarrhea (i.e., greater than 7 stools per day or requiring intravenous fluids) between 1% to 2% [14-17]. For small-molecule EGFR tyrosine kinase inhibitors like erlotinib, gefitinib, and

lapatinib, however, diarrhea is substantially more common, occurring in up to 60% for all grades and with Grade 3 diarrhea occurring in about 6% to 9% of patients [15].

Although diarrhea is common with EGFR inhibitor treatment and can significantly impact patients' quality of life, evidence suggests that diarrhea is also an indicator that EGFR TKIs are hitting their target [18]. In one study of gefitinib in NSCLC, the presence of diarrhea was identified as one of the independent predictors of a partial response, and the absence of diarrhea was one of the predictors of progressive disease [19]. In another study of gefitinib and erlotinib in patients with recurrent and metastatic squamous cell carcinoma of the head and neck, EGFR TKI-induced diarrhea was associated with clinical benefit and also an association with more favorable overall survival [20]. In afatinib lung cancer trials, a trend toward a higher rate of progression-free survival was observed in patients who had Grade 2 or greater diarrhea in the first 28 days of treatment with afatinib compared with patients who experienced no AEs [21].

Currently, prophylactic loperamide is often given to prevent diarrhea with other EGFR-directed therapies [22]. In addition, based on our experience from a recently completed Phase 2 breast cancer study, it is estimated that the average body size of US patients will be larger than that of the average Korean patient. Therefore, to address the expected issues with acute diarrhea in this study, prophylactic loperamide will be administered with the 24 mg starting dose of poziotinib (Section 5.4.10.1), which was not required in the Korean studies. In addition, intermittent dosing rather than continuous dosing will be used to also help address the more chronic toxicities of rash and stomatitis. Supportive care for mucositis/stomatitis will also be provided, aiming to control symptoms for all patients during the study.

In Phase 1 studies, 18 mg/day was the maximum tolerated dose for continuous dosing, and 16 mg/day was the recommended dose for continuous dosing. Based on the tolerability of poziotinib in patients in this study so far and the previous data, two additional cohorts with lower doses and continuous dosing are being added to this protocol amendment. No new patients will be enrolled into the original 24 mg per day with intermittent dosing cohort (**Cohort 1**) and new patients will be enrolled into **Cohort 2** (16 mg/day, continuous dosing). If patients are unable to tolerate the dosing regimen in **Cohort 2**, new patients will be enrolled into **Cohort 3** (12 mg/day, continuous dosing). These changes are being made in order to improve patient tolerability while maintaining consistent drug exposure.

## 2 STUDY OBJECTIVES

### 2.1 Primary Objective

- To establish the dosing schedule for poziotinib to be used in the clinical development program
- To evaluate the **Objective Response Rate (ORR)** of poziotinib in patients with HER2-positive metastatic breast cancer (MBC)

### 2.2 Secondary Objectives

- To assess the safety and tolerability of poziotinib in patients with HER2-positive MBC
- To evaluate the pharmacokinetics of poziotinib in patients with HER2-positive MBC
- To evaluate other efficacy variables of poziotinib in patients with HER2-positive MBC, including the following:

- **Progression-Free Survival (PFS)**
- **Disease Control Rate (DCR)**
- **Time to Progression (TTP)**

### 3 INVESTIGATIONAL PLAN

#### 3.1 Study Design and Treatment Plan

This is a Phase 2, open-label, multicenter study to establish the dose regimen and evaluate the preliminary efficacy and the safety / tolerability of poziotinib in approximately 75 patients with HER2-positive MBC who have received at least two prior HER2-directed treatment regimens including trastuzumab and T-DM1.

The **Screening** period (**Day -30 to Day -1**) lasts up to approximately 30 days prior to **Cycle 1, Day 1**. Patients must meet all Inclusion/Exclusion Criteria to participate in the study. Eligible patients will provide written Informed Consent prior to undergoing any study procedures.

Each treatment cycle is 21 calendar days in duration. Eligible patients will be enrolled into each dose cohort as described below. In Amendment 1, in addition to the original 24 mg cohort (**Cohort 1**), two additional treatment cohorts were added.

- **Cohort 1:** 24 mg (three 8-mg tablets once daily) for 2 weeks, rest 1 week (ENROLLMENT COMPLETE)
- **Cohort 2:** 16 mg (two 8-mg tablets once daily) continuous dosing
- **Cohort 3:** 12 mg (one 8-mg tablet and two 2-mg tablet once daily) continuous dosing

Patient enrollment in **Cohort 1** is complete. New patients will begin enrollment into **Cohort 2**. Rules for safety review and enrollment for **Cohort 2** and **Cohort 3** follow:

#### **Cohort 2:**

- Rate of Grade 3 or greater AEs of special interest (ie, diarrhea, skin rash, stomatitis) that are identified during Safety Data Review after the first 6 patients and again after 12 patients have completed **Cycle 1**:
  - **>33%:** Stop **Cohort 2** ( $\geq 3$  of 6 or  $\geq 5$  of 12 patients with Grade 3 or above AE of special interest) and begin **Cohort 3**
  - **$\leq 33\%$ :** Keep enrolling **Cohort 2** until 30 patients are enrolled and treated and no additional patients will be enrolled.

#### **Cohort 3 - only if Cohort 2 is stopped due to toxicity:**

- Rate of Grade 3 or greater AEs of special interest (ie, diarrhea, skin rash, stomatitis) are identified during Safety Data Review after the first 6 patients and again after 12 patients have completed **Cycle 1**:
  - **>33%:** End enrollment in **Cohort 3**
  - **$\leq 33\%$ :** Keep enrolling **Cohort 3** until 20 patients are enrolled and treated

Toxicity will be assessed based on the grade of the adverse events using CTCAE version 4.03.

[figure not shown]
All treatments will be taken orally, once daily (QD) at approximately the same time each morning. On **Day 1** of each cycle, the patient's absolute neutrophil count (ANC) must be

$\geq 1.0 \times 10^9/L$  and platelet count must be  $\geq 100 \times 10^9/L$  before administering poziotinib. For **Cycle 1** and **Cycle 2** only, the ANC and platelet count should also be confirmed prior to the dose on **Day 8**. **Day 1** of a new cycle is equivalent to **Day 22** of the previous cycle, with a window of  $\pm 3$  days for the visit. If a visit is delayed during 1 cycle, then all subsequent cycles will be delayed sequentially.

All patients will be treated until disease progression, death, intolerable adverse events, or up to a maximum of 24 months, whichever comes first.

The study design diagram is presented in **Figure 2**, and the Schedule of Study Assessments and Procedures is presented [Appendix 1](#).

**Figure 2 Study Design Diagram**

### 3.2 Study and Treatment Duration

The total duration of the study will be approximately 3 years. The duration of study participation for each patient includes the following segments:

- **Screening Period:** 30 days
- **Treatment Period:** 21 days per cycle for up to 24 months
- **End-of-Treatment Visit:** 35 ( $\pm 5$ ) days after the last dose of poziotinib

## 4 PATIENT POPULATION

### 4.1 Inclusion Criteria

1. Patient, or patient's authorized representative, must be willing and capable of giving written Informed Consent and must be able to adhere to dosing and visit schedules as well as meet all study requirements.
2. Patient has histopathologically confirmed primary breast cancer with metastatic lesions.
3. Patient has confirmed HER2 overexpression or gene-amplified tumor via immunohistochemistry [IHC] with IHC 3+ or IHC 2+ with confirmatory fluorescence *in situ* hybridization [FISH]+.
4. At least two prior HER2-directed therapy regimen(s) for breast cancer, including trastuzumab and trastuzumab emtansine (T-DM1, KADCYLA®).
5. Patient is at least 18, and  $\leq 90$  years of age.
6. Patient has adequate hematologic, hepatic, and renal function, as defined by:
  - Absolute neutrophil count (ANC)  $\geq 1.0 \times 10^9/L$ .
  - Platelet count  $\geq 100 \times 10^9/L$
  - Hemoglobin  $\geq 9$  g/dL
  - Total bilirubin  $\leq 1.5$  mg/dL, if hepatic metastases are present,  $\leq 2.5$  mg/dL
  - Aspartate aminotransferase/serum glutamic-oxaloacetic transaminase (AST/SGOT), alanine aminotransferase/serum glutamic-pyruvic transaminase (ALT/SGPT), and gamma-glutamyltransferase (GGT)  $\leq 2.5 \times$  upper limit of normal (ULN); if hepatic metastases are present  $\leq 5.0 \times$ ULN
  - Creatinine  $\leq 2.2$  mg/dL or calculated creatinine clearance  $\geq 40$  mL/min
7. Patient has an Eastern Cooperative Oncology Group (ECOG) performance status  $\leq 2$ . Life expectancy is more than 6 months.
8. Patient has measurable disease, as per the Response Evaluation Criteria in Solid Tumors (RECIST, version 1.1).
9. Patient is willing to practice 2 forms of contraception, one of which must be a barrier method, from study entry until at least 30 days after the last dose of poziotinib.
10. Females of childbearing potential must have a negative pregnancy test within 30 days prior to enrollment. Females who are postmenopausal for at least 1 year (defined as more than 12 months since last menses) or who are surgically sterilized do not require this test.

### 4.2 Exclusion Criteria

1. Patient has had previous treatment with poziotinib prior to study participation.
2. Patient has brain metastases that are symptomatic or require therapy to control symptoms, as well as any history of radiation, surgery, or other therapy, including steroids, to control symptoms from brain metastases within 15 days of enrollment.
3. Patient has received anticancer chemotherapy, biologics, immunotherapy, cure-intent radiotherapy, or investigational treatment within 15 days, except for hormone therapy, palliative therapy, or supportive therapy.

4. Patient has a history of congestive heart failure (CHF) Class III/IV according to the New York Heart Association Functional Classification or serious cardiac arrhythmias requiring treatment.
5. Patient has a cardiac ejection fraction <50% by either echocardiogram or multi-gated acquisition (MUGA) scan.
6. Patient has a history of other malignancies within the last 5 years, except for non-melanoma skin cancer or carcinoma *in situ* of the cervix.
7. Patient is confirmed to have clinically significant or recent acute gastrointestinal disease presenting as diarrhea and/or colenteritis as a main symptom (ie, acute enteritis, malabsorption, or Common Terminology Criteria for Adverse Events (CTCAE, version 4.03) Grade 2 or above diarrhea due to other etiologies).
8. Patient is unable to take drugs orally due to disorders or diseases that may affect gastrointestinal functions, such as inflammatory bowel diseases (eg, Crohn's disease, ulcerative colitis) or malabsorption syndrome, or procedures that may affect gastrointestinal functions, such as gastrectomy, enterectomy, or colectomy.
9. Patient has an active liver disease or biliary tract disease (except for Gilbert's disease, asymptomatic biliary stones, liver metastasis, or stabilized chronic liver diseases).
10. Patient has an active uncontrolled infection, underlying medical condition, or other serious illness that would impair the ability of the patient to receive protocol treatment.
11. Patient has active bleeding disorders, uses warfarin or other coumadin-derived anticoagulants, has abnormal International Normalized Ratio (INR), or abnormal prothrombin time test within one month prior to the study.
12. Patient is pregnant or breast-feeding.

### 4.3 Patient Discontinuation/Withdrawal Criteria

Patients can withdraw from participation in this study at any time, for any reason, specified or unspecified, and without prejudice.

All treated patients must be withdrawn from the study at 24 months or for the following reasons:

- Development of an adverse event (AE) that interferes with the patient's participation
- Initiation of non-protocol therapy
- Development of progressive disease (PD)
- Patient withdrawal of informed consent
- Delay of poziotinib administration for >42 days since last study drug administration
- Investigator decision
- Sponsor decision
- Lost to follow-up
- Pregnancy
- Death

The reason for the patient discontinuing study treatment or terminating from the study must be recorded on the case report form (CRF). Patients who discontinue treatment or who are

withdrawn from treatment will return for an **End-of-Treatment Visit** 35 ( $\pm$ 5) days after the last dose of poziotinib or prior to beginning a new treatment, whichever is first.

## 5 STUDY PROCEDURES

The study design diagram is presented in **Figure 2**, and the Schedule of Study Assessments and Procedures is presented **Appendix 1**.

### 5.1 Screening

Informed Consent is to be obtained prior to the start of any protocol-specified assessments or procedures. The procedures and evaluations required for enrollment into the study are summarized below. All potential study patients will be screened and eligibility determined prior to enrollment. The results of any procedures or laboratory assessments performed prior to the signing of Informed Consent as part of the site's routine standard of practice will be allowed for use as a Screening Assessment at the discretion of the Sponsor. This information is to be discussed with the Medical Monitor before the patient is enrolled in the study. All procedures are to be performed as outlined in **Appendix 1** prior to the start of study treatment, unless otherwise noted.

### 5.2 Patient Assignment

Each patient who signs an Informed Consent Form for participation in this study will be assigned a unique screening number according to the instructions in the study binder.

Confirmation of eligibility is to be received by the investigational site from Spectrum prior to enrollment of a patient. After a patient has signed the ICF, the Investigator or site staff should assign a Patient ID. The Patient ID will include two parts: the site number assigned by Spectrum will be comprised of 5 digits with a 2-digit alphabetic country code [Reference ISO 3166] followed by a 3-digit site specific numeric code and a 3-digit patient sequential number, unique to a site, separated by a hyphen (ie, ██████████).

A CRF will only be completed for patients who are enrolled and receive a Patient ID.

### 5.3 Timing of Assessments and Procedures

#### 5.3.1 Screening (Day -30 to Day -1)

The following screening assessments should be performed within 30 days of **Cycle 1, Day 1**. Obtain Informed Consent prior to any study procedures.

- Informed Consent
- Relevant medical history
- Demographic data
- Height and weight
- Complete physical examination
- Vital signs
- Eastern Cooperative Oncology Group (ECOG) Performance Status assessment

- Complete blood count (CBC) with 5-part differential and platelets prior to poziotinib administration (may be obtained up to 7 days prior to **Cycle 1, Day 1**)
- Prothrombin time/International Normalized Ratio (as needed, and only for those patients who may have bleeding disorders and are using warfarin or other coumadin-derived anticoagulants)
- Serum biochemistry prior to poziotinib administration (may be obtained up to 7 days prior to **Cycle 1, Day 1**)
- Pregnancy test (urine beta-human chorionic gonadotropin [ $\beta$ -HCG]) in women of childbearing potential
- Echocardiogram or MUGA scan to evaluate cardiac ejection fraction
- Tumor histopathology report (from local pathologist)
- Tumor assessment (may be obtained prior to signing of IC and may be used for **Screening** purposes as long as it is performed prior to **Cycle 1, Day 1**; consultation with the Sponsor is required)
- Hormone-receptor status, including ER, PR and HER2, number of nodes, and stage
- Adverse event assessment using NCI CTCAE, version 4.03, record AEs related to study procedures only
- Concomitant medications

### 5.3.2 Treatment Period – Cycle 1, Day 1

- Eligibility confirmation
- Patient ID
- Height and weight
- Physical examination
- Vital signs
- ECOG Performance Status assessment
- Pharmacokinetic blood sampling:
  - Sparse PK blood sampling taken pre-dose and at 1 hour and 2 hours ( $\pm 15$  min) post-dose  
OR
  - Intensive PK blood sampling pre-dose and 30 minutes, 1, 1.5, 2, 3, 4, 6, and 24 hours post-dose (**if consented**)
- Dispense poziotinib and loperamide
- Adverse event assessment using NCI CTCAE, version 4.03, record AEs related to study procedures only
- CBC with 5-part differential and platelets
- Dispense Patient Diary
- Concomitant medications review

### 5.3.3 Treatment Period – Cycle 1, Day 8 ( $\pm 1$ Day)

- Complete blood count with 5-part differential and platelets
- Adverse events using NCI CTCAE, Version 4.03, record AEs related to study procedures only
- Patient Diary Collection
- Concomitant medications

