**Adverse Event and Serious Adverse Event Reporting:**

Adverse events will be recorded from the first dose of study drug administration until 35 ( $\pm 5$ ) days after the last dose of study drug is administered. From the time Informed Consent is signed to the first dose of study drug administration, only serious adverse events (SAEs) related to study procedures will be recorded and reported.

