### 5.3.4 Treatment Period – Cycle 1, Day 14 ( $\pm 3$ Days) (Cohort 1 only)

- Sparse PK blood sampling collected pre-dose
- Adverse event assessment using NCI CTCAE, Version 4.03, record AEs related to study procedures only (Cohorts 2 and 3 by telephone)
- Concomitant medications (Cohorts 2 and 3 by telephone)

### 5.3.5 Treatment Period – Cycle 2, Day 1

- Weight
- Physical examination
- Vital Signs
- ECOG Performance Status assessment
- Complete blood count with 5-part differential
- Serum biochemistry
- Sparse pharmacokinetic blood sampling taken pre-dose and at 1 hour and 2 hours ( $\pm 15$  min) post-dose
- Dispense poziotinib
- Adverse event assessment using NCI CTCAE, Version 4.03, record AEs related to study procedures only
- Patient Diary Collection
- Concomitant medications

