### 5.3.6 Treatment Period – Cycle 2, Day 8 ( $\pm 1$ Day)

- Complete blood count with 5-part differential and platelets
- Adverse event assessment using NCI CTCAE, Version 4.03, record AEs related to study procedures only
- Patient Diary Collection
- Concomitant medications

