## 7 SAFETY ASSESSMENT

### 7.1 Safety Measures

It is the responsibility of the Principal Investigator to oversee the safety of the patients at their site and to report all AEs/SAEs that are observed or reported during the study, regardless of relationship to study drug or clinical significance. The decision to modify the dose of study treatment will be determined by the Investigator based on the decision rules shown in [Section 6.1.5](#).

Safety data will also be reviewed on a regular basis by Spectrum's study monitoring team, which includes a Clinical Research Associate (CRA), Medical Monitor, and other personnel from the company or its designee.

Adverse events will be characterized by intensity (severity), causality, and seriousness by the Investigator based on the regulatory definitions included below.

This study will utilize the National Cancer Institute (NCI) Common Terminology Criteria for Adverse Events (CTCAE) Scale Version 4.03 for AE grading.

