## 7.2 Adverse Events

An AE is defined as any untoward medical occurrence in a patient or clinical investigation patient, temporally associated with the use of a medicinal product, whether or not considered related to the medicinal product. Therefore, an AE can be any unfavorable and unintended sign (including an abnormal laboratory finding), symptom, or disease (new or exacerbated) temporally associated with the use of a medicinal product. A treatment-emergent AE (TEAE) is any AE that occurs from the first dose of study treatment until 35 ( $\pm 5$ ) days after the last dose of study treatment.

The study will record all AEs according to the information in [Section 7.3](#).

Examples of AEs **include**:

- Exacerbation of a chronic or intermittent pre-existing condition including either an increase in frequency and/or intensity of the condition.
- New conditions detected or diagnosed after investigational product administration.
- Signs, symptoms, or the clinical sequelae of a suspected drug interaction.
- Signs, symptoms, or the clinical sequelae of a suspected overdose of either investigational product or a concurrent medication.
- AEs may include pre-treatment or post-treatment events that occur as a result of protocol-mandated procedures, ie, invasive procedures.

Abnormal laboratory results are to be recorded as AEs, if any of the following conditions are met:

- The abnormal laboratory value leads to a therapeutic intervention.
- The abnormal laboratory value is considered to be clinically significant by the Investigator.
- The abnormal laboratory value is predefined as an AE in the protocol or in another document communicated to the Investigator by Spectrum or designee.

Examples of events that **do not** constitute AEs include:

- Medical or surgical procedures (eg, endoscopy, appendectomy); the condition that leads to the procedure is an AE.
- Situations where an untoward medical occurrence does not occur (eg, social and/or convenience admission to a hospital).
- Anticipated day-to-day fluctuations of pre-existing disease(s) or condition(s) present or detected at the start of the study that do not worsen.
- Planned and prescheduled hospitalizations and procedures.
- Progressive disease.

The adverse events of special interest identified with poziotinib treatment in this study include diarrhea, skin rash, oral cavity mucositis/stomatitis, fatigue, and vomiting/nausea.

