### 7.3 Guidelines for Recording and Attribution Scoring of Adverse Events

Timely and complete reporting of all AEs is required for all patients. Monitoring and documentation of all AEs allows for identification of potential study-drug or dose-related AEs, and for adherence to regulatory requirements. Please refer to the CRF Completion Guidelines located in the study binder for detailed instructions for AE reporting.

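### Six treatment-visit lists (Protocol 5.3.2 to 5.3.7) limit AE recording to procedure-related events, while the synopsis, Protocol 7.1 and 7.3.1, and SAP 5.4.2 require all AEs from first dose

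*Protocol*

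**What the plan says.** **Visit lists.** Protocol 5.3.3 (Cycle 1, Day 8) reads "Adverse events using NCI CTCAE, Version 4.03, record AEs related to study procedures only". Sections 5.3.1 (Screening) and 5.3.2 (Cycle 1, Day 1) both carry "Adverse event assessment using NCI CTCAE, version 4.03, record AEs related to study procedures only". Section 5.3.4 (Cycle 1, Day 14) has the limit with a note on mode of contact: "record AEs related to study procedures only (Cohorts 2 and 3 by telephone". Sections 5.3.5, 5.3.6 and 5.3.7 repeat it, for example "Adverse event assessment using NCI CTCAE, Version 4.03, record AEs related to study procedures only" at Cycle 2, Day 8. The End-of-Treatment list (5.3.8) asks for an AE assessment with no limit.

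**Recording rules.**
- The synopsis states "Adverse events will be recorded from the first dose of study drug administration until 35" (±5) days after the last dose.
- Protocol 7.1 makes the investigator responsible to "report all AEs/SAEs that are observed or reported during the study, regardless of relationship to study drug or clinical significance".
- Protocol 7.2 sends the reader to 7.3: "The study will record all AEs according to the information in" that section.
- Protocol 7.3.1 puts every AE from first dose onto the AE CRF. It confines the period between consent and first dose to procedure-related SAEs. SAP 5.4.2 says the same.
- In the Appendix 1 schedule, the limit is footnote k. It is attached to the Screening column only and refers to SAEs.

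**The concern.** The two sets of instructions cannot both be followed after first dose. On Cycle 1, Day 1 the limit could be read as covering the pre-dose part of the visit. From Day 8 onward it has no such reading.

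The data at stake are central to the study. Protocol 8.6 names TEAE incidence as a primary safety outcome measure. The Cohort 2 rule in Protocol 3.1 counts patients with Grade 3 or greater diarrhea, rash or stomatitis at two safety reviews, and so bears on the primary objective of establishing the dosing schedule. If some of the approximately 35 centers followed Section 5.3 and others Section 7, recording would differ between sites and TEAE incidence would be understated. The SAP (Section 3) reports that Cohort 2 continued after both reviews but gives no counts, so a reader cannot judge how close either came to its limit.

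**Working it through.** The plan states no figure to reproduce. The check compares texts, followed by arithmetic for scale.

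**1. The instructions side by side**

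| Time | Section 5.3 lists | Synopsis, Protocol 7.3.1, SAP 5.4.2 |
|---|---|---|
| Screening (5.3.1) | procedure-related AEs | procedure-related SAEs only |
| Cycle 1, Day 1 (5.3.2) | procedure-related AEs | SAEs only before dose; all AEs after |
| Five later lists (5.3.3 to 5.3.7) | procedure-related AEs | all AEs |
| End of treatment (5.3.8) | no limit | all AEs |

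Lists for treatment visits that carry the limit: 6. Wholly after first dose: 5. Lines to align, counting 5.3.1 for its AE/SAE mismatch: 6 + 1 = 7.

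**2. Which rule is intended.** Section 7.2 points to 7.3, footnote k limits Screening alone, and the dose-modification rules in 6.1.5 and Table 2 depend on counting Grade 3 or greater AEs by occurrence. All three point to Section 7. The likely explanation is that the Screening wording was carried into the treatment visits.

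**3. Which events are exposed.** SAEs must reach the sponsor within 24 hours (7.7). Abnormal examination findings go onto the AE CRF (5.4.2), which covers much of rash and stomatitis. For Cohort 2, three post-dose contacts bear on Cycle 1: Day 8, Day 14 and Cycle 2, Day 1. The examination route reaches two of them, because Day 14 is by telephone. What remains is mainly non-serious events known from history, chiefly Grade 3 diarrhea.

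**4. Margin of the Cohort 2 rule (Protocol 3.1: stop at 3 or more of 6, or 5 or more of 12)**
- First review: 3/6 = 50.0% stops; 2/6 = 33.3% continues.
- Second review: 5/12 = 41.7% stops; 4/12 = 33.3% continues.

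One uncounted patient reverses the decision, but only if the review was at its limit.

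**5. Size of the exposed group.** Protocol 1.1.5 lists only rash (59%) and mucosal inflammation (26%) as Grade 3 TEAEs at 25% or more in the earlier 16 mg/day continuous study (N = 39). Grade 3 diarrhea was therefore below 25%: 10/39 = 25.6% is too many, so at most 9/39 = 23.1%. Assuming a similar rate in Cohort 2:
- first 6 patients: 0 to 6 × 9/39 = 1.4 expected with Grade 3 diarrhea;
- first 12 patients: 0 to 12 × 9/39 = 2.8.

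Missed diarrhea changes the count only in a patient with no other recorded qualifying event. Treating rash as independent (an assumption), the ceilings fall to 6 × 9/39 × (1 − 0.59) = 0.6 and 12 × 9/39 × 0.41 = 1.1, before any allowance for mucosal inflammation. These rates cover all treatment, not Cycle 1, and the earlier Korean studies did not require prophylactic loperamide (Protocol 1.2). They give scale only.

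**6. Sensitivity of the rule to incomplete recording.** Let p be the true per-patient probability of a qualifying event in Cycle 1 and c the share of such patients who are counted. With q = pc, the exact binomial probability of stopping is

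P(stop) = P(X₆ ≥ 3) + Σ over x = 0, 1, 2 of P(X₆ = x) · P(Y₆ ≥ 5 − x), where X₆ and Y₆ are independent Bin(6, q).

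| True rate p | c = 100% | 75% | 50% | 25% |
|---|---|---|---|---|
| 33% | 0.444 | 0.228 | 0.076 | 0.010 |
| 40% | 0.633 | 0.361 | 0.130 | 0.018 |
| 50% | 0.844 | 0.567 | 0.234 | 0.034 |

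Both p and c are assumed; the documents give neither.

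**The case against.** The best reply is that this is misplaced Screening text and that the protocol already settles which rule governs. Section 5.3 is about the timing of procedures, and 7.2 refers recording to 7.3. Sites also had separate instructions, the "CRF Completion Guidelines located in the study binder for detailed instructions for AE reporting", which may have been correct.

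Further records make silent loss less likely. Concomitant medications are reviewed at these visits, including the Day 14 telephone contact, and new ones go on the CRF (5.4.10). A Grade 3 or greater AE calls for treatment to be withheld (6.1.5), and the SAP summarises the first interruption and dose reductions (5.4.1). The sponsor also reviews safety data regularly (7.1, 9.4.1). Finally, the SAP, with approval dated 1/4/2021, reports enrollment and both reviews as past, so new wording would help few patients, if any.

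Much of this stands. The intended rule is clear, the likely loss is smaller than the raw diarrhea figures suggest once overlap with rash is allowed for, and correcting the text cannot alter the completed reviews. The Screening mismatch alone is minor, since it leads only to over-collection. But neither document gives Section 7 precedence over the visit lists, and the CRF guidelines are not available here. A medication entry or dose interruption does not replace an AE record in a TEAE table or a review count. These records are useful sources for a check rather than a reason to omit one.

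**Conclusion.** The concern holds and should be fixed. The contradiction is certain: six treatment-visit lists, five wholly after first dose, conflict with the synopsis, Protocol 7.1 and 7.3.1, and SAP 5.4.2. Its effect on the data is unknown, and nothing in the documents shows that any AE was missed.

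The plausible exposure is narrow: non-serious events reported by history, chiefly Grade 3 diarrhea. The effect on Cohort 2 could be decisive only if a review stood at its limit and the missed patient had no other qualifying event. That the documents are silent on the review counts is not itself a fault in the SAP, but it means the text alone cannot rule this out.

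**What to change.** 1. Align the AE lines in Protocol 5.3.1 to 5.3.7 with 7.3.1: procedure-related SAEs only before first dose, and all AEs regardless of relationship from first dose. The sentence in 8.6 on pre-treatment AEs can be brought into line with SAP 5.4.2, which says SAEs, at the same time.
2. Before database lock (assumed still to come, as the documents give no date), confirm that AE data were collected under 7.3.1. Use the source verification already planned in 9.1, 9.2.1 and 9.5.1. Compare source notes with the AE CRF for Cycle 1 of the first 12 Cohort 2 patients, starting with Grade 3 or greater diarrhea. Use concomitant-medication and dose-interruption records as pointers, and diaries where they hold symptom entries (their content is not described).
3. Extend the check to the remaining patients only if gaps are found: 33 + 34 = 67 enrolled, less 12, leaves 55.
4. Report any change to the 6-patient and 12-patient review counts in the study report.

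The cost is seven lines of text, plus the optional one in 8.6, and a focused check of 12 patients. If routine verification has not already covered this, that check is some added monitoring work. It needs no new visit, procedure or patient.
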